10.1 SOC Adverse Events

Since this a post market study involving commercially available SOC dressings of FDA cleared and approved medical devices; adverse events associated with their use may also require reporting to FDA.

An AE is defined as any unfavorable or unintended sign, symptom or disease that occurs or is reported by the subject to have occurred, or a worsening of a pre-existing condition related to the procedure or medical treatment (device/drug) used. All AEs related to the study procedure or medical treatment, including intercurrent illnesses, must be recorded in the subject's medical records and on the CRF. CTCAE v4.0 will be used for AE reporting.

AEs will be defined as those events that occur after the first study treatment is applied at TV1, through the final study visit. A description of the AE along with the onset date, end date, severity, action taken, treatment, outcome, likely cause and relationship to the study procedure or products will be recorded in the CRF.

AEs associated with each treatment arm will be tabulated and compared at the end of the study. AEs will be elicited through direct questioning, subject reports, and physical examination.

An abnormal laboratory test result is not by itself considered to be an AE unless the Investigator considers the finding of clinical significance that should be reported in such a manner.

The Investigator is responsible for assessing the relationship of the AE to the procedure or medical treatments used and the seriousness and expectedness of the AE at the time of occurrence. A medically qualified person appointed by the Sponsor will also assess this once the Sponsor has been notified of an AE. All AEs that occur during the trial will be documented on the AE CRF.

AEs reported during the study should be followed to resolution of the AE or within thirty days from the end of the study. A final assessment of the outcome will be made at that time.

Each AE related to the study procedure or medical treatment used will be categorized as "serious" or "not serious," based on the definition of a serious adverse event (SAE). An SAE is defined as an AE resulting in at least one of the outcomes described in Section 10.1.3.

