3.00Pe	Group 2: SOC primary dressing with FIBRACOL™
Study Design	Multi-center, open label, randomized controlled trial
Sample Size	For this RCT, N = up to 240 subjects
Centers	Up to 15 centers within the United States, Open/competitive enrollment.
Endpoints	Primary endpoint: - The proportion of subjects that obtain complete closure over the 12-week treatment period Secondary endpoints: - The time to achieve complete wound closure of the target ulcer by the end of 12 weeks
	 Percentage wound area reduction from TV1 to TV13 measured weekly with digital photographic planimetry and physical examination
	The number and type of Treatment Emergent Adverse and Serious Adverse Events
	 Change in peripheral neuropathy of the target foot assessed using the standard 10-point Semmes-Weinstein monofilament exam [Time Frame: TV1, TV3, TV7, TV9, and EOS1]
	 Change in pain in the target ulcer assessed using the NPRS scale. [Time Frame: TV1, TV3, TV7, TV9, and EOS1]

Confidential Page 10 of 73

Version 2.0 Date: May 12, 2023 Change in quality of life using WOUND-Q assessment [Time Frame: SV1, TV3, TV7, EOS1] **Exploratory Endpoint:** Difference in cellulitis and/or infection at 12 weeks Use of near-infrared tissue oxygenation imaging assessment of wounds at select sites to evaluate changes in vascularization/oxygenation of wounds with treatment (Kent Imaging SnapshotNIR: Time Frame: SV1, TV1 pre-randomization, TV2, TV4, TV7, and EOS1. Safety There is no formal safety objective for this study as MIRRAGEN™ and FIBRACOL™ are commercially available, 510K FDA cleared dressings for diabetic foot wounds. Therefore, in accordance with FDA regulations, adverse reactions to the dressings will be recorded and provided to the study Sponsor for required FDA reporting and will be concurrently reported to all Investigators and IRBs. Adverse events associated with application of standard of care dressing will be collected during the course of the study. Collection and reporting of any adverse reaction data, in accordance with FDA regulations and adverse events associated with dressing application will ensure study subject safety.

Surveillance Schedule

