8.4.2 Medical History

A medical history will be recorded during the Screening Period and will include:

- All ongoing medical conditions
- All previously resolved medical conditions related to diabetes or foot ulceration or which are relevant in the opinion of the Investigator

Events that emerge prior to the randomization visit will be recorded in the medical history and not as Adverse Events. Aside from being used to determine subject eligibility, this information will permit the Investigator to record the nature, duration and severity of any ongoing baseline medical conditions that occur prior to randomization

Medical histories will be recorded using the body system categories outlined below:

Cardiovascular

Respiratory

Gastrointestinal

Renal

Hepatic

Neurological

Endocrine

Lymphatic

Hematologic

Immunologic

Dermatologic

Psychiatric

Genitourinary

Other

DFU History

For each relevant history, the following will be documented:

- Disease/disorder/condition
- Date of diagnosis
- History status (resolved or ongoing)

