10.1.3 Serious Adverse Events

A SAE is any untoward medical incident that occurs during the course of the study beginning after informed consent has been executed.

A SAE is defined as any AE that:

- Results in death
- Is life threatening (the subject is at immediate risk of dying from the adverse experience)
- Requires subject hospitalization or prolongs existing hospitalization
- Results in persistent or significant disability/incapacity
- Is a congenital anomaly/birth defect

Note: Important medical events that may not result in death, be life-threatening, or require hospitalization may be considered a SAE when, based upon appropriate medical judgment,

Confidential Page 52 of 73

they may jeopardize the subject and may require medical or surgical intervention to prevent one of the outcomes listed in this definition.

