10.1.3.1 Reporting of Serious Adverse Events

The Investigator or delegated site personnel is required to report all SAEs that occur during the study. Once the Investigator or delegated site personnel becomes aware of an SAE, he/she must report the SAE to the CRO and/or ETS Wound Care, LLC, the study Sponsor, within 24 hours.

The study sponsor contact is: [name]: ETS Wound Care. LLC, [contact] email: [contact]

The CRO contact information is listed on the SAE reporting form.

A written SAE report must follow and must include a full description of the event and all supporting documentation available at the time (e.g., lab reports, culture reports, etc.). Additional follow-up information as it becomes available must be reported to the CRO and / or Sponsor.

The Investigator or delegated site personnel is also responsible for reporting all SAEs to the IRB in accordance with local laws and regulations. The Investigator is responsible for maintaining documentation in the study file that indicates the IRB has been properly notified.

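### The AE and SAE rules contradict each other on whether relatedness decides what is recorded and graded, and on whether a serious event during screening is an SAE

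*Combined protocol and SAP*

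**What the plan says.** **Recording.** Section 10.1 states "All AEs related to the study procedure or medical treatment, including intercurrent illnesses, must be recorded" in the medical record and on the CRF. Further down the same section it states "All AEs that occur during the trial will be documented on the AE CRF". The Safety row of the synopsis says that "adverse reactions to the dressings will be recorded and provided to the study Sponsor" and that "Adverse events associated with application of standard of care dressing will be collected during the course of the study".

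**Seriousness.** Section 10.1 closes with: "Each AE related to the study procedure or medical treatment used will be categorized as" serious or not serious. Earlier in that section the Investigator is to assess the seriousness of an AE, with no condition on relatedness. Under Section 10.1.3.1 the Investigator or delegate "is required to report all SAEs that occur during the study".

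**Start points.** Section 10.1 counts AEs from the first application of study treatment at TV1. Section 8.4.2 says: "Events that emerge prior to the randomization visit will be recorded in the medical history and not as Adverse Events". Section 10.1.3 describes an SAE as "any untoward medical incident that occurs during the course of the study beginning after informed consent has been executed", and then defines it as an AE that meets one of the listed outcomes.

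**Use of the data.** Section 3 lists the number and type of treatment-emergent AEs as a secondary endpoint for comparison between groups. The synopsis version also names serious events. Section 10.1 says that AEs will be tabulated by arm and compared.

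**The concern.** A between-arm comparison of AEs is only as good as the rule that admits events to it. Here one statement of the rule admits every AE, and others speak only of events linked to the dressing or procedure. Section 10.1.2 gives the relatedness decision to the Investigator, and the trial is open label. If relatedness is applied when the event is recorded, the person deciding whether it counts knows which dressing the subject received, and the excluded events leave no trace on the AE form. Section 9.2 also gives adverse effects or events particular weight in the interim analysis, so the same counts would be used there.

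The start-point conflict raises a different issue: whether a hospitalization during screening, for example, is reported as an SAE or entered only as medical history.

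**Working it through.** The plan states no figure to reproduce on this point. The check is a comparison of the texts.

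**1. Which AEs are recorded**

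| Place | Rule |
|---|---|
| Synopsis, Safety | Reactions to the dressings; AEs linked to applying the dressing |
| Section 10.1, recording sentence | Related AEs, with intercurrent illnesses included |
| Section 10.1, AE CRF sentence | All AEs |
| Section 10.1.2 | Has a Not Related category, which covers intercurrent events |
| Section 8.10.3 | Every ulcer infection after randomization goes on an AE CRF, with no relatedness test |
| Sections 4.5.3.3 and 4.5.4 | Sites ask about any change in health and any AE |

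The first two rows are narrow and the rest are broad. The recording sentence also conflicts with Section 10.1.2: it counts intercurrent illnesses among related AEs, while Section 10.1.2 files intercurrent events as not related. The AE definition in Section 10.1 is ambiguous too, since its phrase about being related to the procedure or treatment may qualify every event or only the worsening of a pre-existing condition.

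**2. Which AEs are graded for seriousness**

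The categorization sentence covers related AEs. The Investigator's assessment duty in the same section covers AEs without that condition, and the reporting duty in Section 10.1.3.1 covers all SAEs. An unrelated hospitalization after TV1 must therefore be reported, yet the categorization sentence does not provide for classifying it.

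**3. When SAEs start**

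- Consent is taken at SV1, and SAEs run from then (Section 10.1.3).
- AEs run from the first treatment at TV1 (Section 10.1), and earlier events are not AEs (Section 8.4.2).
- The visit schedule requires at least 14 days between SV1 and TV1, and its AE assessment row is blank for SV1, SV2 and TV1.
- An SAE must be an AE (Section 10.1.3).

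For at least 14 days, then, a serious event lies inside the SAE window but cannot meet the SAE definition. Debridement and other protocol procedures take place during that time.

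**4. Size of any bias in the comparison**

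Suppose a proportion *p* of each arm truly has an AE, and the fractions of those subjects with an event judged related are *r*₁ and *r*₂. A site that records related events only would show a difference of *p*(*r*₁ − *r*₂) where the true difference is zero. In absolute size that can lie anywhere from 0 to *p*. The documents give none of *p*, *r*₁, *r*₂ or the share of sites that would follow the narrow wording, so no figure can be put on it.

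**The case against.** The best defence is that the protocol, read as a whole, intends full recording. The narrow sentence says that related AEs must be recorded; it does not say that others are to be left out. The AE CRF sentence, the relationship field, the Not Related category, the infection rule and the visit checklists all point the same way, and the introduction to Section 10 makes the Investigator document any event that meets the definition. This stands. A reader might infer that the plan restricts AE recording to related events, but the documents do not support that.

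Nor do they support the inference that serious events judged unrelated will go unreported. Section 10.1.3.1 requires all SAEs to be reported within 24 hours, and a medically qualified person appointed by the Sponsor also assesses each notified AE. That second assessment is a partial safeguard, because it cannot recover an event that was never recorded.

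On start points, different windows for AEs and SAEs are acceptable in themselves, and entering a screening event in medical history does not forbid reporting it as an SAE. What remains is a mismatch of definitions. A reader might also think that screening events distort the arm comparison. They cannot, because pre-treatment events fall outside a treatment-emergent count.

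Finally, Section 9.2 reserves hypothesis testing for the primary and selected efficacy endpoints and lists no AE test, and the synopsis states no formal safety objective. No efficacy conclusion is at risk. The AE comparison is still a listed secondary endpoint.

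**Conclusion.** The collection rules are wrong as written because they conflict on three matters: whether unrelated AEs are recorded, whether they are graded for seriousness, and whether a serious event during a screening period of at least 14 days is an SAE. The intention was probably full recording, but a site could follow the narrow wording and believe that it complied. The first two conflicts bear on a between-arm secondary endpoint in an open-label trial, and the third on safety reporting only. Any bias depends on some sites following the narrow wording and on relatedness being judged differently by arm. The documents show neither, and its size cannot be computed from them. The primary endpoint is unaffected. The wording should be corrected, since events not captured during conduct may not be recoverable later.

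**What to change.** - **Section 10.1:** delete the relatedness condition from the recording sentence and from the seriousness sentence. Clarify what the relatedness phrase in the AE definition qualifies.
- **Synopsis, Safety:** replace the collection wording about reactions to the dressings and events linked to dressing application with collection of all AEs from first treatment. Keep relatedness as a separate field.
- **Sections 8.4.2, 10.1, 10.1.3 and the visit schedule:** reconcile these so that serious untoward events from consent onward are reported under Section 10.1.3.1, with pre-treatment ones listed apart from the treatment-emergent comparison. The AE row of the schedule needs a matching entry or note for SV1, SV2 and TV1.

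The cost is edits in these places and some additional unrelated events on the existing AE form. If full recording was already intended, the recording and seriousness edits do not change that intention.

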published 40-patient pilot study in DFU which demonstrated a statistically significant 2.8 fold increase in healing rates compared to SOC alone (p=0,004) and doubled the rate of wound are reduction at all time points $(p-0.027)^{22}$.

Confidential Page 15 of 73

2 Rationale for Study

MIRRAGEN™ is a bioactive borate-based glass fiber matrix (BBGFM) that can dissolve in wound fluids over a period of several days. A recent 40-patient RCT and additional case studies involving the treatment of chronic diabetic foot ulcers (DFUs) with BBGFM suggest that when used as dressing as part of the standard of care (SOC), improved healing trajectories result. Based on this early promising data, a larger RCT is necessary to further validate these results. For consistency one type of wound will be studied in this trial and we have chosen DFU's as they are some of the most common wounds seen in the wound clinics.

Confidential Page 16 of 73

3 Study Endpoints

The purpose of this clinical evaluation is to collect patient outcome data on 2 commercially available standard of care dressings in partial/full-thickness diabetic foot ulcer subjects. Patient outcomes will be compared at 6 and 12 weeks.

The **primary endpoint** is the proportion of subjects that obtain complete closure over the 12-week treatment period.

Secondary endpoints include a comparison between groups of the following clinical measures:

- 1. The time to achieve complete wound closure of the target ulcer by the end of 12 weeks.
- 2. Percentage wound area reduction from TV1 to TV13 measured weekly with digital photographic planimetry and physical examination.
- 3. The number and type of Treatment Emergent Adverse Events.
- 4. Change in peripheral neuropathy of the target foot assessed using the standard 10-point Semmes-Weinstein monofilament exam [Time Frame: TV1, TV3, TV7, TV9, and EOS1].
- 5. Change in pain in the target ulcer assessed using the NPRS scale. [Time Frame: TV1, TV3, TV7, TV9, and EOS1].
- 6. Change in quality of life using WOUND-Q assessment.

Exploratory/Tertiary Endpoints

- 7. Difference in cellulitis and/or infection at 12 weeks.
- 8. Use of near-infrared tissue oxygenation imaging assessment of wounds at select sites to evaluate changes in vascularization/oxygenation of wounds with treatment (Kent Imaging SnapshotNIR; Time Frame: SV1, TV1 pre-randomization, TV2, TV4, TV7, and EOS1).

Confidential Page 17 of 73

4 Study Design

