4.2 Phase 2: Treatment

The Treatment Phase (up to 13 weeks) begins with a series of assessments designed to confirm the subject's continued eligibility. Investigators will debride the ulcer, in accordance with SOC if required. Subjects whose ulcers continue to meet eligibility criteria will then be randomized to one of two groups: (1) SOC with MIRRAGEN™ primary dressing or (2) SOC with FIBRACOL™ primary dressing. Additionally for the most compassionate care subjects in either group whose ulcers have demonstrated wound area reduction by less than 50% at week 7 of treatment will be considered a treatment failure and will be permitted to obtain additional outside treatment and thus will be exited from the study.

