4.3 Subject Treatment Assessments

4.3.1 DFU Assessments

During the Treatment Phase, subjects will be evaluated on a weekly basis. Weekly patient outcome evaluations include the Investigator's assessment of ulcer healing and measurements of ulcer size using digital imaging to measure wound area and provide photos of wounds, including photos of healed wounds for adjudication.

Note: All procedures required during baseline are included in TV1 prior to the Randomization visit.

Other evaluations during the Treatment Phase are detailed in the procedures section.

Subjects will be seen weekly (± 3 days) until the ulcer is healed or they meet protocol criteria to exit the study.

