4.5 Study Schedule

The study is divided into two phases: Screening and Treatment Phases. The schedules for the protocol-specified assessments and procedures in each phase are detailed in the following sections. Note that there is an end of study visit (EOS1) scheduled on Week 13 or

Confidential Page 21 of 73

earlier if the wound heals or does not demonstrate at least 50% wound area reduction at 6 weeks after randomization (Week 7) and a follow-up visit (HCV1) to confirm that a wound is healed two weeks after first being assessed as healed.

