9.1 Data Analysis

This study consists of primary, secondary and exploratory/tertiary (research) endpoints. Data analysis of study endpoints includes use of validated DFU wound healing measures, quantitative and qualitative analyses, as well as exploratory methodologies. Table 4 below details each study endpoint, corresponding data, and planned analyses.

TABLE 4: ETS WOUND CARE, LLC DFU ENDPOINT DATA ANALYSIS

Endpoint	Endpoint Description	Supporting Study Data	Endpoint Analysis
Primary	Comparison of the proportion of index ulcers "healed" at 12 weeks	Investigator assessment of healing (100% epithelization w/no drainage), measurements of ulcer size using digital imaging and photos	Adjudication panel will determine using photographs of the DFU
	Proportion of Index Ulcers healed at 6 weeks		
	PAR at 6 and 12 weeks	Digital imaging	Mathematical wound area change
	Time to healing within 6 and 12 weeks	Primary endpoint	Mathematical time based on healing
Secondary	Changes in peripheral neuropathy	Semmes Weinstein with vibratory	Mathematical change in scores
	Changes in wound quality of life	WOUND-Q (Quality of life tool)	Mathematical change in scores
	Change in pain levels during trial	NPRS	Mathematical change in scores
	Difference in cellulitis and/or infection at 12 weeks	Observation	Count of positive and negative responses
Exploratory/Tertiary	Changes in tissue perfusion of wound bed and periphery with treatment	SnapshotNIR	Exploratory

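### Adverse event counts are compared between arms without allowing for outcome-dependent follow-up, so a difference in either direction may reflect time observed

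*Combined protocol and SAP*

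**What the plan says.** - **Endpoint.** Section 3 lists, among the secondary measures compared between groups, "The number and type of Treatment Emergent Adverse Events". The synopsis adds serious events.
- **Window and method.** Section 10.1: "AEs will be defined as those events that occur after the first study treatment is applied at TV1, through the final study visit". The only analysis given is that "AEs associated with each treatment arm will be tabulated and compared at the end of the study". The thirty-day rule in the same section follows events already reported; it does not look for new ones.
- **When observation ends.** Section 4.3.1: "Subjects will be seen weekly (± 3 days) until the ulcer is healed or they meet protocol criteria to exit the study". Section 4.5 brings the end-of-study visit forward at healing, or at six weeks after randomization when area reduction is below 50%. Section 4.2 says that such a subject "will be considered a treatment failure and will be permitted to obtain additional outside treatment and thus will be exited from the study".
- **After closure.** Section 4.5.5 puts a general AE check in the healing confirmation visit two weeks later. Table 1 (schedule of visits) marks the AE row at that visit with footnote [A], which limits the assessment to reopening.
- **Statistics.** Section 9.2 assumes closure of 0.70 v 0.35 with 120 per arm, lists six secondary analyses of which none concerns AEs, and gives AEs as a particular object of the interim look at about 100 subjects. Table 4 in Section 9.1 has no AE row; the related infection endpoint is a "Count of positive and negative responses". Detailed methods are left to a SAP to be written before database lock.

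**The concern.** A count of events depends on the event rate and on how long subjects are watched. Here the second factor is set by the healing outcome, which the trial expects to differ greatly between arms. Earlier closure shortens observation, and so does failing the 50% check at TV7. The first shortens it mainly in the arm that heals better, the second mainly in the arm that heals worse. A table of counts by arm therefore mixes risk with exposure, and the reader has no denominator with which to separate them. A real excess of events could be masked, or an apparent difference produced where none exists. The same holds for the interim review.

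**Working it through.** **The plan's own figure.** The documents give no AE rate or exposure figure. The closure proportions come from the power statement in Section 9.2. Power for 120 per arm, 0.70 v 0.35, two-sided alpha 0.049, computes to 0.9999, which agrees with the stated 100%.

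**Inputs.** From the documents: closure 0.70 and 0.35; exit at week 6; confirmation two weeks after closure; otherwise about 12 weeks. Assumed, because the documents give nothing: mean closure week 5 to 7 (MIRRAGEN) and 7 to 8 (FIBRACOL); TV7 exits 10% to 20% and 20% to 55% of all subjects. Withdrawals and reopened wounds are ignored.

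**Formula.** Mean weeks = closed × (mean closure week + 2) + exits × 6 + remainder × 12.

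- MIRRAGEN, shortest: 0.70 × 7 + 0.20 × 6 + 0.10 × 12 = 7.3
- MIRRAGEN, longest: 0.70 × 9 + 0.10 × 6 + 0.20 × 12 = 9.3
- FIBRACOL, shortest: 0.35 × 9 + 0.55 × 6 + 0.10 × 12 = 7.65
- FIBRACOL, longest: 0.35 × 10 + 0.20 × 6 + 0.45 × 12 = 10.1

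Ratio of mean observation, MIRRAGEN to FIBRACOL: 7.3/10.1 = 0.72 up to 9.3/7.65 = 1.22.

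These are corners. At 0.72 the share of non-healers leaving at TV7 is 0.20/0.30 = 67% with MIRRAGEN but 0.20/0.65 = 31% with FIBRACOL; at 1.22 it is 0.10/0.30 = 33% v 0.55/0.65 = 85%. With 50% of non-healers leaving in both arms and closure at weeks 5 and 8, the figures are 0.70 × 7 + 0.15 × 6 + 0.15 × 12 = 7.6 and 0.35 × 10 + 0.325 × 6 + 0.325 × 12 = 9.35, a ratio of 0.81.

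**Second model.** Take healing times as exponential, truncated at 12 weeks. The mean is 1/λ − 12(1 − p)/p with λ = −ln(1 − p)/12, giving 4.82 weeks (p = 0.70) and 5.57 weeks (p = 0.35). Let q be the share of non-healers who leave at week 6, and c the weeks of AE observation after closure. Mean weeks = p(mean + c) + (1 − p)(6q + 12(1 − q)).

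| c | q, MIRRAGEN v FIBRACOL | Mean weeks | Ratio |
|---|---|---|---|
| 2 | 0 v 0 | 8.38 v 10.45 | 0.80 |
| 2 | 0.5 v 0.5 | 7.48 v 8.50 | 0.88 |
| 2 | 1 v 1 | 6.58 v 6.55 | 1.00 |
| 2 | 0.25 v 0.75 | 7.93 v 7.52 | 1.05 |
| 2 | 0.5 v 1 | 7.48 v 6.55 | 1.14 |
| 0 | 0 v 0 | 6.98 v 9.75 | 0.72 |
| 0 | 1 v 1 | 5.18 v 5.85 | 0.89 |

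For scale only: at an illustrative 2 events per 100 subject-weeks in both arms, the first row is 1005 v 1254 subject-weeks and 20.1 v 25.1 expected events; the fifth is 897 v 786 and 17.9 v 15.7. The true rate ratio is 1.00 in each.

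**Why the confirmation visit matters.** Counting to it adds 0.70 × 2 = 1.4 weeks per MIRRAGEN subject and 0.35 × 2 = 0.7 per FIBRACOL subject, so the conflict between Section 4.5.5 and footnote [A] itself alters the balance of time at risk.

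**The case against.** The case against has weight. The synopsis states that there is no formal safety objective, and Section 9.2 confines hypothesis tests to the primary and selected efficacy endpoints. Its Hochberg statement mentions all endpoints, but no AE test is listed for it to act on. Tabulating and comparing could include percentages of subjects with an event, or rates, and the unwritten SAP could add exposure. Events per course of treatment is also a legitimate target: fewer weeks in a dressing because the wound closed is a consequence of treatment. And a per-week rate assumes roughly constant risk, which is doubtful if wound events cluster while the ulcer is open.

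This bears on the form of the point and of the remedy, not on the gap. Descriptive counts also mislead without a denominator, and a SAP still to be written is the place to supply one. The counts should stay, with rates and time-based summaries beside them.

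A reader might infer more than the documents support:

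- **That the faster-healing arm must show fewer events.** The TV7 exit removes poor responders and mainly shortens follow-up in the slower arm. It can cancel the difference (1.00) or reverse it (1.05 to 1.14 in the second model).
- **That AE observation ends at closure.** Section 4.5.5 has an AE check two weeks later, though footnote [A] narrows it.
- **That a false-positive rate can be quoted.** It would need an AE test and an AE rate, and the plan states neither.

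**Conclusion.** The point holds as a risk of bias in either direction. A named between-group secondary endpoint is a count, each subject's AE window ends at an outcome-dependent visit, and no section gives subject-time, a rate or a common AE window. On the planned closure proportions and the assumed ranges, the ratio of mean observation runs from about 0.72 to 1.22, and with one weekly AE rate in both arms the expected counts follow it. The extremes need uneven exit shares among non-healers. With equal shares and counting to the confirmation visit, the second model gives 0.80 to 1.00. Closure times, exit shares and constant risk are assumptions; only 0.70, 0.35 and the visit rules come from the documents. Neither the direction nor the size can be fixed in advance. This is a worthwhile, cheap improvement and does not affect the primary analysis.

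**What to change.** In Section 10.1 and the SAP:

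1. Keep AE counts and the number of subjects with an event.
2. Define time at risk and report subject-weeks by arm.
3. Add events per subject-week with confidence intervals, for example from a Poisson or negative binomial model with log observation time as offset, and time to first event.
4. Apply the same to the interim AE review.
5. State that the rates assume roughly constant risk, which is why the time-based summaries accompany them. Where an events-through-week-6 table is shown, say that it removes the effect of TV7 exits but not of early healing.
6. Reconcile Section 4.5.5 with footnote [A] of the visit schedule on what is assessed at the healing confirmation visit, because this determines where time at risk ends.

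The cost is one more table, some SAP wording and an added modelling assumption. Section 10.1 already has AE onset dates recorded, and visits are documented, so no new data are needed.
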